### 1.3 SCHEDULE OF ACTIVITIES

	Prior to enrollment Time 0; Day -1 (-30)	Clinic Visit Time 1; Day 1	Post-clinic Time 2; Day 1 (+10)	Time 3; Day 2 – Day 30	Time 4; Day 30 (+21)	Time 5; Day 120 ± 21	Time 6; Day 210 ± 21
Electronic Record Review	X						
Informed Consent	X						
'Opt-in' 4-week text message program	X						
Baseline Questionnaire (e.g., past EBT utilization, smoking behavior, mediators, moderators)	X						
Study brochure		X					
Randomization		X					
Control & Intervention Videos		X					
Text Messages-Control				X			
Text Message-Intervention				X	X	X	X
Outcome Evaluation							
Satisfaction with intervention/post video questionnaire			X				
Follow-up Questionnaires (e.g., mediators, self- reported EBT contact and utilization, quit attempts)					X	X	X
Objective confirmation of contact and utilization of EBT resources				X	X	X	X
Biochemical validation of self-reported smoking abstinence					X	X	X
Adverse Events Reporting		X	X	X	X	X	X

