At the teeth cleaning appointment, all participants will receive a Viotek Spectre virtual reality and earbuds with volume control. A study smartphone (iPhone) will be inserted into the headset and programmed to show either the intervention or the control video, depending upon the patient's randomization. Both videos will be the same duration (10 minutes). Participants randomized to the Intervention group will watch one of two videos dependent upon their latest assessment of motivation to quit (assessed at the dental clinic appointment). If the participant is motivated to quit within 30 days, they will watch the "Ready to Quit" video; those not motivated to quit within 30 days will watch the "Not Ready to Quit" video. The RA will help the participant adjust the headset for comfort and use the audio control on the earbuds to ensure the volume is set at a level where the participant is able to hear the practitioner while watching the video. Participants will be advised to raise their hand to signal for adjustments, removal of the headset, or the conclusion of the video.

Shortly after participants complete watching the assigned video, the RA will trigger the post-video questionnaire in REDCap. The post-video questionnaire will be delivered as e-link through text message and email to all participants. Participants will be required to complete this questionnaire in their own time within 10 days of receiving the e-link invitation.

Within 24 hours of randomization, the Intervention group will begin the 4-week text message curriculum program that has been designed in preparatory research to: a) motivate EBT contact and utilization, b) facilitate transition to EBTs, c) dispel myths and misinformation about EBTs, and d) measure mediators weekly. There are two different tracks of text messages to motivate EBT contact and utilization: one for those who are motivated to quit and one those who are not motivated to quit. The Control group will receive assessment-only text messages, and will follow the same schedule as the assessment text messages in the intervention group (e.g., one text message to assess motivation, one to assess self-efficacy, and one to assess outcome expectancies each week for three weeks). All participants will be able to connect to, and access the services of, one or more EBT resources at any point during the study: both groups receive this information at the dental clinic visit via brochure, and the Intervention group

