will receive additional information via text messaging. At the conclusion of both text message programs (Intervention text messages and Control group assessment-only text messages), participants will complete an end-of-treatment assessment (*Time 4*, immediately after the end of the text message program 4-weeks post-randomization). Follow-up assessments will occur at *Time 5* (3-months post end-of-treatment assessment), and at *Time 6* (6-months post end-of-treatment assessment). Participants who self-report quitting smoking at any of these assessments will be asked to provide a saliva sample for biochemical verification of smoking abstinence. Samples will be assayed for cotinine; smoking abstinence is defined as cotinine values < 15 ng/mL.

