regard to compensation, participants will receive \$50 for completing baseline assessment activities (\$30 for baseline assessment, given at the end of the appointment; \$20 for the post-appointment satisfaction questionnaire to be completed via e-link), and \$30 for each completed follow-up (1 month-end of text message, and 3-and 6-months later) as well as a \$10 bonus if they complete each assessment within two weeks of the deadline. We will send participants a 'compensation chart' so they can be reminded of the various points at which they will receive compensation for completing the surveys.

The retention schedule for each survey is detailed below:

Survey	REDCap reminders	Manual reach outs frequency	Type of contact
Baseline	Email: Days 2, 4, 6 from survey invitation as long as dental appointment is still pending	Day 8 from survey invitation as long as dental appointment is still pending	Phone call and voicemail
	Text: Days 2,4,6 from survey invitation as long as dental appointment is still pending	Two days before dental appointment	Text message only
		Day before dental appointment	Phone call, voicemail, and text message
Post-video	Email: Days 2, 4, 6 from survey invitation	Day 8 from survey invitation	Phone call and voicemail
	Text: Days 2,4,6 from survey invitation	Day 10 from survey invitation (final day)	Phone call, voicemail, and text message
1 month, 3 month, and 6 month	Email: Days 3, 6, 9, 12 from survey invitation	Day 1 from survey invitation	Retention letter
		Day 8 from survey invitation	Phone call and voicemail

	Text: Days 3, 6, 12 from survey invitation	Day 13 from survey invitation (last chance to earn \$40 before 2 weeks is over!!)	Phone call, voicemail, and text message
		Day 18 from survey invitation	Text message including hyperlink to REDCap survey only
		Day 20 from survey invitation (last chance to earn \$30 before 3 weeks!!)	Phone call, voicemail, and text message

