- EBTs for smoking cessation will be operationalized as: 1) utilization of any EBT over the 7-month study period; 2) total number of EBTs utilization during the 7-month study period (ranging 0 to 4); 3) EBT utilization index score (UIS; obtained by first computing a proportion of utilization score for each of the EBTs for each participant, and then adding up the individual proportion scores; see section 9.4.1 for details); 4) combination of at least one form of non-pharmacologic EBT and at least one form of pharmacologic EBT over the 7-month study period.
- Quit smoking attempts (assessed at Time 4 – 6). The number of quitting smoking attempts participants have made, since last contact, that have lasted 24 hours or more and that were not due to hospitalization or illness.
- Motivation to quit smoking (assessed at Time 4 – 6). Participants' motivation to quit smoking within 30 days (yes vs no).
- Smoking abstinence (assessed at Time 4 – 6). Seven-day point-prevalence abstinence (7-day ppa) assessed by self-report of no smoking, not even a puff, in the past 7 days and salivary cotinine level < 15 ng/mL.
- Mediators of treatment effects (assessed at Time 2 – 6). Theoretically driven constructs hypothesized to mediate any observed intervention effect (EBT utilization, quit smoking attempts, motivation to quit, or smoking abstinence) include the social cognitive theory constructs of motivation, self-efficacy, and outcome expectancies.
- Moderators or treatment effects (assessed at baseline). Moderating factors include sex, race or ethnicity, perceived stress and readiness to quit smoking.

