#### 9.4.9 EXPLORATORY ANALYSES

Aim 4. Mediation. Exploratory analyses will examine the role of social cognitive factors as mediators of the intervention effect on any EBT utilization. Our analyses will account for the temporal precedence assumption of mediation. If participants utilize the EBT within one month of their dental appointment, we will compute change from baseline to the time point prior to first initiation of any EBT. If participants contact an EBT after the first month, we will compute change scores between baseline and end of treatment (1-month post-appointment). Our primary approach to establishing mediation effects will be the product of coefficients method, which utilizes a multiple mediation model to simultaneously test the effects of the potential mediators. Corresponding standard errors will be calculated using bootstrapping (10,000 bootstrapped sample). Multiple mediation allows for simultaneous testing of the

Based on the NIH Behavioral and Social Intervention Clinical Trial Protocol Template v3.0 - 20180827

effect of a set of mediators while controlling for the effects of the others, and a comparison of the effects of the mediators to determine the relative influence of each mediator.

Aim 4. Effect modification. We will explore whether the Intervention has different effects on any EBT utilization over the 7-month study period for different subpopulations by examining interactions between potential moderators and intervention using logistic regression models. We will examine perceived stress, readiness to quit smoking at baseline, gender, and race/ethnicity as potential effect modifiers.

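### For EBT contacts after month 1, the mediation rule in section 9.4.9 can use a mediator reading taken after the contact it is meant to precede

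*Combined protocol and SAP*

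**What the plan says.** Section 9.4.9 states the governing principle: "Our analyses will account for the temporal precedence assumption of mediation". It then splits EBT users at one month.

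- **Contact within the first month:** "we will compute change from baseline to the time point prior to first initiation of any EBT". This reading is tied to the contact.
- **Contact after the first month:** "If participants contact an EBT after the first month, we will compute change scores between baseline and end of treatment (1-month post-appointment"). This reading is tied to a visit, with no condition on the date of contact.

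Section 1.3 heads the end-of-treatment column "Time 4; Day 30 (+21"), a window that opens on Day 30 and extends only later. Section 4.1 gives the nominal timing as "immediately after the end of the text message program 4-weeks post-randomization". Section 5.5 has staff still pursuing the one-month survey on Day 20 after invitation, so completion well into the window is planned for.

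On contact, section 4.1 says "All participants will be able to connect to, and access the services of, one or more EBT resources at any point during the study". On measurement, section 8.1 says "Mediators of treatment effects (assessed at Time 2 – 6"). Section 4.1 adds weekly text-message assessments of all three constructs for three weeks, on the same schedule in both arms.

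**The concern.** A mediator has to be measured before the outcome it is supposed to produce. The first-month rule guarantees this by construction; the later rule guarantees it only if Time 4 is completed on the day the window opens. Between Day 31 and Day 51 a participant can make first contact and then fill in Time 4.

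Motivation, self-efficacy and outcome expectations could plausibly change once someone has started treatment. If so, part of the association between mediator and EBT use would run from EBT use to mediator, and the product of coefficients would inherit it. Section 2.1 lists testing mechanisms of change among the study's contributions, so this analysis is likely to be reported and read.

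**Working it through.** **1. Can the order reverse under the rule as written?** The last permitted Time 4 day is 30 + 21 = Day 51. Contact on Day 33 is after the first month, so the later rule applies. Time 4 on Day 45 is inside the window. The mediator is then read 45 − 33 = 12 days after contact. No section excludes or re-dates such a reading. Section 1.3 also puts mediators and self-reported EBT contact on the same follow-up questionnaire. A first contact made after month 1 and self-reported at Time 4 cannot have come after that Time 4 mediator reading.

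**2. How many EBT users?** The plan gives no figure to reproduce. From section 9.2: 364 analysed (455 less 20%), 182 per arm, any EBT 22.7% v 37.6%. Expected EBT users are 182 × 0.227 + 182 × 0.376 ≈ 110. Contact timing and Time 4 lag are assumptions; here Time 4 is uniform over Days 30–51.

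- *Contacts uniform over 210 days:* share in the window is 21/210 = 10%. Half of these precede Time 4, so 5% of users, about 5 or 6 people.
- *Front-loaded contacts (exponential with scale θ, truncated at Day 210):* share in the window is (e^(−30/θ) − e^(−51/θ)) / (1 − e^(−210/θ)). For θ = 40 this is (0.472 − 0.279)/0.995 = 19%; for θ = 60 it is (0.607 − 0.427)/0.970 = 18–19%. The reversed share is e^(−30/θ)/(1 − e^(−210/θ)) × [1 − (θ/21)(1 − e^(−21/θ))], which gives 0.475 × 0.222 = 10.5% and 0.625 × 0.156 = 9.8%. That is about 11 people.

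The share depends strongly on how promptly Time 4 is done. As a share of *post-month-1* contacts, with lag uniform over 0–7, 0–14 or 0–21 days:

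| Contact timing after Day 30 | 0–7 | 0–14 | 0–21 |
|---|---|---|---|
| Even to Day 210 | 2% | 4% | 6% |
| Declining, median 60 days | 4% | 9% | 13% |
| Declining, median 30 days | 8% | 15% | 21% |

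**3. What does it do to the tests?** This was simulated with 182 per arm, an arm effect on the mediator of 0.3 SD, no true mediator effect on EBT use, one mediator, and a lift of 0.5 or 1.0 SD when Time 4 follows contact. The size and sign of the lift are assumptions. Rejection rates at nominal 5%:

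| Test | No lift | Uniform, 0.5–1.0 SD | Front-loaded, 0.5–1.0 SD |
|---|---|---|---|
| Mediator-to-EBT path alone | about 5% | 6–8% | 7–15% |
| Indirect effect, product / normal-theory SE | about 1% | 1–2% | 2–4% |
| Indirect effect, joint significance | 4% | 5–6% | 6–12% |

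Repeat runs agree to within about one percentage point; one set put the single path at 5–7% under uniform timing.

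The last row can be checked by hand. The arm-to-mediator test has power Φ(0.3/√(2/182) − 1.96) = Φ(2.86 − 1.96) ≈ 0.82. Multiplying by the single-path rate gives 0.82 × 5% ≈ 4% with no lift and 0.82 × 15% ≈ 12% in the worst setting. Joint significance approximates a percentile bootstrap interval. The normal-theory row stands in for dividing by a bootstrap standard error. Section 9.4.9 specifies bootstrapped standard errors but not which form of interval or test follows.

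**The case against.** The strongest reply has four parts.

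*The planned test is the indirect effect, not one path.* This stands. A reader might infer from the single-path rates that Hypothesis 4 will tend to look supported when the mediators do nothing. The table does not bear that out. With a normal-theory standard error the indirect-effect test never exceeds 5%. By joint significance it goes clearly above 6% only when contacts are front-loaded and the lift is near 1 SD.

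*Every driver of the bias is assumed.* This also stands. The documents give no contact dates, no Time 4 lags and no effect of EBT use on the mediators. An unconditional statement that the path is biased upward is not supported; the direction follows only if starting an EBT raises the mediators.

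*The intent is clear and the detail can wait.* Section 9.4.9 states temporal precedence as the aim, and section 9.4.1 defers to a formal SAP. A contact first reported on the Time 4 survey might be assigned to the first interval and so to the contact-tied rule. But the text does not say so, and an analyst who followed it literally would use the post-contact reading. The deferred SAP is a reason to settle the wording now.

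*The analysis is exploratory.* Correct. The synopsis numbers Hypothesis 4 among the secondary hypotheses, but the objectives and sections 9.1 and 9.4.9 treat mediation as exploratory. Nothing here touches the primary estimate or its power.

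**Conclusion.** The stated rule does not deliver the stated property. For first contacts on Days 31–51 that come before Time 4 completion, the mediator is read after the outcome, and nothing elsewhere in the protocol corrects this. That conclusion rests on the text alone.

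The size rests on assumptions: about 5% of EBT users with uniform contact times, about 10% with front-loaded ones, and fewer if Time 4 is usually completed promptly. If EBT use lifts the mediators by 0.5–1.0 SD, the mediator-to-EBT path is inflated to about 6–8% or 7–15%. For the planned indirect effect, inflation is material only in the combination of front-loaded contacts, a lift near 1 SD and a percentile-type interval, at about 11–12%.

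This is a narrow, correctable gap in an exploratory analysis. It does not bear on the primary comparison, and it does not show that a positive mediation result would be spurious.

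**What to change.** In section 9.4.9, or in the formal SAP before unblinding, apply the first-month rule to all EBT users. The change score uses Time 4 only if its completion date is before the date of first EBT contact. Otherwise it uses the last mediator reading completed before that contact (a weekly text assessment or Time 2). Wherever the dates are known, post-contact readings then fall to zero, and users whose Time 4 came first are unaffected. State at the same time which bootstrap interval will be used, since the consequence depends on it.

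The cost is a sentence or two, with two downsides.

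- Some later users get an earlier reading, possibly from the text-message measure instead of the questionnaire. The documents do not say that the two instruments match.
- The rule needs a date of first contact. For clinic programs and medication obtained outside the quitline, which are self-reported, the documents do not say that a date is captured. The existing first-month rule already needs that date, so the requirement is not new, but the SAP should say how it is met.

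A landmark at Time 4 that counts only later contacts would also restore the order, but it is not recommended. Under the front-loaded assumptions, 41–53% of first contacts fall by Day 30 and would be discarded, and the outcome would no longer be any EBT use over 7 months.

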attempts and increase their motivation to quit; 2) To test the efficacy of the Intervention vs. Controls on biochemically verified smoking abstinence. Hypothesis 3 states: Participants in the Intervention will achieve higher rates of point-prevalence abstinence at follow-up; 3) To assess the mechanisms through which intervention effects occur (mediators such as self-efficacy, motivation, and outcome expectations) and to identify subpopulations for whom intervention effects differ (moderators such as gender and motivation to quit). Hypothesis 4 states: The Intervention will directly affect the putative mediators of intervention effect, which will in turn affect EBT engagement (contact) and utilization. The role of moderators will be exploratory.

Participants will be randomized (1:1) at the dental clinic, after receiving the study brochure and before watching the videos during their teeth cleaning. Randomization will be implemented by employing a stratified block procedure with small, random size blocks and will be stratified by motivation to quit (ready to quit smoking in 30 days vs. not ready to quit within 30 days). To avoid randomization errors, randomization will be configured within REDCap, the secure web application used to build and manage the questionnaires and study forms which is programmed and managed by the BU Biostatistics and Epidemiology Data Analytics Center (BEDAC). A biostatistician will build the randomization program. The study RA will trigger randomization by pressing the feature on the REDCap eCRF form using an iPad. All dental providers will be masked to treatment condition because both the Intervention group and the Control group will be watching a video through the VR headset. Only the PI, project director, statistician, and study RA who is in the clinic will be unmasked to treatment condition.

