## 9.2 SAMPLE SIZE DETERMINATION

Power calculations focus on the comparison of those randomized to the Intervention vs. Control on our primary outcome of any EBT engagement through a chi-square test at the two-sided  $\alpha = 0.05$  level. We will not adjust p-values for multiple comparisons.

Using the odds ratio as our effect size, we estimate the effect of the Intervention will be  $OR=2.05$  (corresponding to percent with any EBT utilization of 22.7% in the Control vs. 37.6% in the Intervention). Only two published studies tested the efficacy of an intervention on EBT utilization rate, both at 12-months follow-up. Brooks et al reported an EBT utilization rate (i.e., Quitline or clinic-based program) of 29.8% in the intervention group vs. 14.7% in controls ( $OR=2.4$ ). Fu et al reported an EBT utilization rate (counseling or medications) of 44.2% in the intervention and 30.6% in controls ( $OR=1.8$ ). Therefore, we use the average EBT utilization rate in the control groups from these studies (22.7%) as our ‘any EBT utilization’ rate under the null hypothesis in the power analysis. Because neither of the above studies used video or were conducted in a dental setting, we also considered previous studies testing the effectiveness of videos on cessation, which report ORs of 1.9 and 3.0, and previous studies on cessation in dental settings (meta-analysis  $OR=2.38$ ). Based on all the above, we conservatively chose an anticipated effect size of  $OR=2.05$  (corresponding to rates of 22.7% vs. 37.6%). With  $\alpha=0.05$  (two-sided), we need a total sample of  $n=300$  subjects to achieve 0.80 power of detecting this anticipated effect. However, because of potential differences between clinic sites, and assuming an attrition rate of 20% (lost to follow-up or ineligible post-randomization), in consultation with the NIDCR in April 2024 we received authorization to increase the sample size to  $n=455$  subjects ( $n=227$  for intervention and  $n=228$  for control group). Therefore, with  $\alpha=0.05$ , the anticipated effect size of  $OR=2.05$ , and 364 subjects (455 minus 20% lost to follow-up or ineligible post-randomization), we will have 0.87 power to detect the anticipated effect.

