### 9.4 STATISTICAL ANALYSES

#### 9.4.1 GENERAL APPROACH

For descriptive statistics, categorical data will be presented through percentages and continuous variables will be presented through means and standard deviations. For statistical tests, a two-tailed  $p$ -value less than 0.05 or a 95% confidence interval not including the null value will be used for statistical significance.

EBT utilization will be analyzed by computing a utilization index score (UIS). The UIS will be created by first computing a proportion of utilization score for each of the EBTs for each participant. For example, a participant who completed 4 of 5 quitline calls has a proportion score of 80. For NRT, the recommended length of treatment is 8 weeks and the proportion completed by each participant will be computed. For the NCI smoke-free text message program, the recommended length of participation is 56 days, and we will compute the proportion of days completed, as well as the proportion of text messages responded to (of those that required a response). For clinic-based programs, the proportion will be calculated as the number of sessions attended divided by maximum number of sessions offered at the corresponding clinic. Because participants may use one or more EBT programs, the overall “utilization index score” will be the sum of the above individual proportion scores of each EBT for each person. These individual scores will be summed to obtain the UIS (continuous variable). The distribution of our UIS will be examined for approximate normality, and transformations to improve normality or categorization of the index score will be considered if appropriate. For primary analyses, we will control for age, gender, and race/ethnicity, along with variables identified through preliminary analyses as significantly differing between study groups.

This study will be registered with Clinical Trials.gov prior to the start of participant enrollment.

A formal Statistical Analysis Plan (SAP) will be completed prior to the completion of the study and the unblinding of the study data.

---

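### Section 9.4.9 enters each mediator as a raw change from baseline without stating the baseline mediator as a covariate, so the Aim 4 indirect effects can be biased by an amount the documents do not fix

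*Combined protocol and SAP*

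**What the plan says.** Section 9.4.9 sets two change windows. For participants who use an EBT within a month of the appointment, the change runs from baseline to the last point before first use. For those who make contact later, "we will compute change scores between baseline and end of treatment (1-month post-appointment"). The method is then given: "Our primary approach to establishing mediation effects will be the product of coefficients method", with several mediators fitted together, 10,000 bootstrap samples and a comparison of the mediators' relative influence. The only adjustment mentioned is for the other mediators.

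The baseline values exist. The schedule of activities in section 1.3 lists "Baseline Questionnaire (e.g., past EBT utilization, smoking behavior, mediators, moderators") before the clinic visit. Randomisation "will be stratified by motivation to quit (ready to quit smoking in 30 days vs. not ready to quit within 30 days"), so one aspect of baseline motivation is also a design factor (section 4.1).

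Age, gender and race/ethnicity are stated as covariates for the primary and secondary models (sections 9.4.1 to 9.4.3), not for mediation. Section 9.4.5 would treat a baseline variable as a potential confounder in later analyses if it differed significantly between arms. A formal SAP is still to be written (section 9.4.1).

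**The concern.** Randomisation protects the comparison of arms, including the arm-to-mediator path. It does not protect the mediator-to-EBT path, which compares participants who changed more with participants who changed less. Change is usually negatively related to starting level. Smokers who begin motivated or confident have less room to rise, yet may be more likely to use an EBT. If so, baseline level confounds the path in the negative direction.

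At stake is Hypothesis 4. A mediator that truly carries the effect could be reported as weak or null. The planned ranking of mediators could also be distorted, because the bias differs with how strongly each baseline predicts EBT use. The section 9.4.5 rule does not help: this confounding is present even when the arms are perfectly balanced at baseline.

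**Working it through.** **The plan's own figure.** The documents give no power or effect size for mediation. The only related figure is for the primary outcome: "corresponding to percent with any EBT utilization of 22.7% in the Control vs. 37.6% in the Intervention", and "364 subjects (455 minus 20% lost to follow-up or ineligible post-randomization), we will have 0.87 power to detect the anticipated effect". With 182 per arm and two-sided alpha 0.05:

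z = [0.149 x sqrt(182) - 1.96 x sqrt(2 x 0.3015 x 0.6985)] / sqrt(0.227 x 0.773 + 0.376 x 0.624) = (2.010 - 1.272) / 0.640 = 1.15, so power = 0.875.

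The stated 0.87 is reproduced. N = 364 is used below only to size illustrations.

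**Algebra.** Let M0 and M1 be the mediator at baseline and follow-up, D = M1 - M0, and let the outcome depend on b x M1 + g x M0. Since M1 = D + M0, this equals b x D + (b + g) x M0. With M0 in the model, the coefficient on D is b. Without M0, the model in effect sets g = -b.

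Take SD(M0) = 1, SD(M1) = k and correlation r. On the linear scale, the fraction of b kept when M0 is omitted is

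[k^2 - k r + (g/b)(k r - 1)] / (k^2 + 1 - 2 k r).

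At k = 1 this reduces to (1 - g/b)/2 for any r. Assumed range for r: 0.3 to 0.7.

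| g/b | k = 0.8 | k = 1 | k = 1.25 |
|---|---|---|---|
| -1 (only change matters) | 1.00 | 1.00 | 1.00 |
| -0.5 | 0.58 to 0.67 | 0.75 | 0.83 to 0.92 |
| 0 (only follow-up level matters) | 0.15 to 0.34 | 0.50 | 0.66 to 0.85 |
| 0.5 | -0.27 to 0.02 | 0.25 | 0.48 to 0.77 |
| 1 (both levels matter equally) | -0.69 to -0.31 | 0.00 | 0.31 to 0.69 |

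**Arm-to-mediator path.** Arm is independent of M0, so both versions are unbiased. With equal SDs the residual variances are 2(1 - r) for change and 1 - r^2 after adjustment, a ratio of 2/(1 + r): 1.54, 1.33 and 1.18 at r = 0.3, 0.5 and 0.7.

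**Logistic check, one mediator.** Assumptions: equal SDs, arm effect on the mediator 0.35 SD, b = 0.5 log-odds per SD, direct effect 0.3 log-odds, event rate about 25%. The true indirect effect is 0.35 x 0.5 = 0.175. Over r = 0.3 to 0.7 (estimates from n = 400,000; power from 1,500 trials of N = 364, both paths significant):

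| g | Change only | With baseline | Power, change only | Power, with baseline |
|---|---|---|---|---|
| -0.5 | 0.174 to 0.178 | 0.173 to 0.178 | 0.80 to 0.90 | 0.82 to 0.91 |
| 0 | 0.084 to 0.085 | 0.174 | 0.34 to 0.49 | 0.82 to 0.91 |
| 0.25 | 0.040 to 0.042 | 0.175 to 0.176 | 0.10 to 0.18 | 0.80 to 0.91 |
| 0.5 | about 0 | 0.174 to 0.177 | 0.03 to 0.05 | 0.81 to 0.92 |

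**Three correlated mediators.** With equal SDs, correlations between mediators of 0.3 to 0.5 (assumed), b = 0.5 for all three and g = 0, 0.25 and 0.5, the change-only coefficients are about 0.16 to 0.20, 0.08 to 0.10 and 0. With all baselines added, each is 0.48 to 0.52. Three equally important mediators would then be ranked strong, weak and null. The first two fall below (b - g)/2 = 0.25 and 0.125 because leaving out predictors also shrinks logistic coefficients.

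**The case against.** The strongest reply is that the plan is silent, not wrong. Section 9.4.9 lists no covariates for mediation, not even the demographic ones used elsewhere, and the SAP is still to come. A reader might infer that baseline adjustment has been ruled out. The documents do not support that; they show only that it is not stated. What remains is that the stated variable is a raw change score, and the one stated route for a baseline mediator to enter, a significant difference between arms, addresses a different problem.

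A reader might also infer that the indirect effect will be halved or will vanish. That does not follow either. Halving needs equal SDs and no direct baseline slope; vanishing needs equal SDs and equal slopes. If EBT use depends only on change, nothing is lost. Ceiling effects tend to make SDs unequal, and the fraction then depends on the correlation too. Against the no-loss case, it requires that, at the same follow-up motivation, those who started more motivated use EBTs less. Section 4.2 leans the other way, describing unmotivated smokers as less likely to take part in intensive interventions. That is suggestive for motivation only and fixes no number.

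Two further limits stand. The simulations use continuous mediators and a fixed window, so their power figures illustrate the mechanism and are not the trial's power. And the argument that a participant already ready to quit cannot become ready applies only if the motivation mediator is the yes/no 30-day item; sections 8.1 and 9.4.3 define that item for the secondary outcome, and the mediator's scale is not stated.

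**Conclusion.** The point holds as a conditional bias in a stated method. Without the baseline mediator, the mediator-to-EBT path and the indirect effect can be misestimated, and the ranking of mediators can be distorted. With equal SDs the retained fraction is (1 - g/b)/2; over the assumed SD ratios of 0.8 to 1.25 and correlations of 0.3 to 0.7, it runs from 1.00 to -0.69. All these inputs are assumptions, so no single figure should be quoted as the size of the loss.

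The consequence is limited. The synopsis lists Hypothesis 4 with the secondary hypotheses, but the synopsis objectives and sections 9.1 and 9.4.9 treat mediation as exploratory. No primary conclusion or sample size changes. It is still worth settling before unblinding, because otherwise the covariates could be chosen after the results are known.

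**What to change.** In section 9.4.9, or in the SAP, state that the baseline value of every mediator enters both models, with the readiness stratum added where it does not duplicate baseline motivation:

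- Mediator model: follow-up mediator (or change) on arm, all baseline mediators and stratum.
- Outcome model: any EBT use on arm, follow-up mediators (or changes), all baseline mediators and stratum.

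The change scores can stay, since with baseline included they give the same mediator and arm coefficients as follow-up scores. Keep the product of coefficients and the 10,000 bootstrap samples. Keep the unadjusted change-score model only as a sensitivity analysis.

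The cost is wording and three or four more covariates. If only change matters and the correlation is high (0.7), adjustment loses some power: about 2 points in one simulation (88.5% to 86.4%, arm effect 0.30 SD) and 5 in the one tabulated above (0.87 to 0.82). At a correlation of 0.3 in that same case it gains 11 to 14 points (0.80 to 0.91; 69% to 83%).

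Also reconcile section 1.3, which places mediators in the baseline questionnaire, with section 8.1, which lists them as assessed at Times 2 to 6. This change does not resolve a separate problem in the same paragraph: the change window depends on when EBT use starts, and none is defined for participants who never use an EBT.
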